3.3 Study Endpoints

3.3.1 Primary Efficacy Endpoint

The primary efficacy endpoint is the Worst-Itch Numeric Rating Scale (WI-NRS) 4-point responder rate at Week 10.

3.3.2 Key Secondary Efficacy Endpoints

The key secondary efficacy endpoints are as follows:

- WI-NRS 4-point responder rate at Week 4
- WI-NRS 4-point responder rate at Week 2

3.3.3 Additional Secondary Efficacy Endpoints

Additional secondary efficacy endpoints are as follows:

- Change from baseline in WI-NRS to other timepoints
- WI-NRS 3-point responder rate at Weeks 2, 4 and 10
- Change from baseline in Dermatology Life Quality Index (DLQI) to Week 10
- Change from baseline in DLQI Question 1 to Week 10
- Change from baseline in Investigator's Global Assessment of PN Activity (IGA PN-A) to Weeks 2, 4 and 10
- Change from baseline in Investigator's Global Assessment of PN Stage (IGA PN-S) to Weeks 2, 4 and 10

3.3.4 *Safety Endpoints*

Safety endpoints are as follows:

- Incidence of TEAEs and SAEs
- Change from baseline in clinical laboratory parameters following study drug exposure
- Change from baseline in vital sign and ECG parameters following study drug exposure
- Change from baseline in the Hospital Anxiety and Depression Scale (HADS)
- Change from baseline in the Epworth Sleepiness Scale (ESS)

3.4 *Safety Review*

3.4.1 *Safety Monitoring Team*

An internal safety monitoring team consisting of representatives from Menlo Therapeutics Inc. and its designees will monitor blinded safety data on a regular basis throughout the study.

4 *SELECTION OF STUDY POPULATION*

4.1 *Study Population*

Approximately 280 adult subjects with pruritus associated with PN will be enrolled in this study.

4.2 *Inclusion Criteria*

Subjects must meet the following criteria to be randomized into the study:

1. Male or female, age 18 years or older at consent.
2. A diagnosis of PN, defined by the presence of at least ten pruriginous nodules secondary to chronic pruritus present on at least two different body surface areas (e.g. both arms, one arm and one leg, one arm and the anterior trunk, or anterior and posterior trunk).
3. The worst pruritus is identified to be within the areas of the PN lesions.
4. Subject has idiopathic PN OR the subject has an identified pruritic condition associated with the PN and has persistent pruritus despite at least 6 weeks of optimized and stable

treatment of the underlying condition prior to the Baseline visit, and is willing to continue the treatment during the study. Please refer to [Section 5.7.1](#).

5. WI-NRS score ≥ 7 in the 24-hour period prior to the Screening visit.
6. Average weekly WI-NRS score ≥ 6.5 in each of the 2 weeks (14 days) immediately prior to Baseline visit, as recorded in the eDiary.
7. All female subjects who are of childbearing potential must be willing to practice highly effective contraception (i.e., pregnancy prevention method with a failure rate of $< 1\%$ per year) from the time of the Screening visit until 5 weeks after last dose of study drug. Please refer to [Section 7.1.5](#) for acceptable methods of contraception.
8. Willing and able (as demonstrated by a $\geq 70\%$ eDiary completion rate in the two weeks prior to Baseline visit) to complete daily eDiary entries within a consistent timeframe for the duration of the study.
9. Willing and able (has adequate cognitive ability, in the investigator's opinion) to comply with study visits and study related requirements including providing written informed consent.

4.3 Exclusion Criteria

Subjects who meet any of the following criteria are not eligible for participation in the study:

1. Prior treatment with serlopitant.
2. Active pruritic skin disease, other than PN, within 6 months prior to randomization (with the exception of acute dermatoses such as contact dermatitis, sunburn, viral exanthem, which have been resolved for longer than 4 weeks). Please refer to [Section 5.7.1](#).
3. Treatment with any of the following therapies within 4 weeks prior to randomization.
 - a. Other NK₁-R antagonists (e.g., aprepitant, fosaprepitant, rolapitant).
 - b. Systemic or topical immunosuppressive/immunomodulatory therapies (including but not limited to corticosteroids, phosphodiesterase-4 (PDE-4) inhibitors, cyclosporine, mycophenolate-mofetil, tacrolimus, pimecrolimus, calcipotriene, methotrexate, azathioprine, interferon-gamma, thalidomide, or phototherapy).
 - c. Systemic therapies with recognized anti-pruritic properties (including but not limited to H1 antihistamines, doxepin, gabapentin, pregabalin, cannabinoids, kappa-opioid receptor agonists, and mu-opioid receptor antagonists (e.g. naloxone, naltrexone)).
 - d. Strong CYP3A4 inhibitors (see [Appendix B](#)).
 - e. Use of an indoor tanning facility, or natural sun exposure resulting in significant tanning or sunburn.
4. Treatment with topical anti-pruritic therapies (e.g., menthol, camphor, pramoxine, capsaicin) within 2 weeks prior to randomization (see [Section 5.7.2](#)).

5. Treatment with biologic therapies within 8 weeks or 5 half-lives prior to randomization, whichever is longer.
6. Treatment with any investigational therapy within 4 weeks (8 weeks for investigational biologic therapies) or 5 half-lives prior to randomization, whichever is longer.
7. Serum creatinine, total bilirubin, alanine aminotransferase (ALT) or aspartate aminotransferase (AST) > 2.5 times the upper limit of normal (ULN) during screening.
8. Untreated or inadequately treated thyroid, adrenal, or pituitary nodules or disease or history of thyroid malignancy.
9. History of malignancy within 5 years prior to randomization, with the exception of actinic keratosis, completely treated and non-metastatic cutaneous basal cell carcinoma or squamous cell carcinoma of the skin.
10. Any known major psychiatric diagnosis, such as major depressive disorder, bipolar disorder, schizophrenia, psychotic disorder, intellectual disability, severe alcohol use disorder, which may confound the assessment of serlopitant safety or efficacy, or interfere with the subject's ability to comply with protocol-mandated activities, within 3 years prior to randomization.
11. Suicidal ideation within 3 years prior to randomization, or any history of suicide attempt.
12. Documented history of parasitic infection, including skin parasites such as scabies, within 8 weeks prior to randomization.
13. Presence of any medical condition or disability that, in the investigator's opinion, could interfere with the assessment of safety or efficacy in this trial or compromise the safety of the subject.
14. History of hypersensitivity to serlopitant or any of its components.
15. Currently pregnant or breastfeeding female subject.
16. Planned or anticipated major surgical procedure or other activity that would interfere with the subject's ability to comply with protocol-mandated assessments (e.g. extended international travel) during the subject's participation in the study.

5 STUDY DRUG

5.1 Study Drug Supply, Route of Administration, and Storage

The study drug in this study is serlopitant 5 mg or placebo in a film-coated tablet formulation for oral administration. The serlopitant tablets contain microcrystalline cellulose, mannitol, croscarmellose sodium, silicon dioxide, sodium lauryl sulfate, and magnesium stearate, and are film coated with Opadry® Brown. The placebo tablets contain microcrystalline cellulose, lactose monohydrate, and magnesium stearate, and are film coated with Opadry® Brown.

The study drug will be provided in bottles that can be stored at room temperature (59-86°F, 15-30°C).

The tablets will be supplied in bottles, with 18 tablets per bottle. One bottle will be issued via Interactive Web Response System (IWRS) at baseline and at Weeks 2 and 4, and two bottles will be issued via IWRS at Week 6. A total of 5 bottles will be dispensed to subjects completing 10 weeks of study drug treatment.

Additional details regarding study drug supplies can be found in the Pharmacy Manual.

5.2 Labeling and Study Drug Accountability

The study drug will be appropriately packaged and labeled in bottles with 18 tablets per bottle. The study drug supplied for this study is not to be used for any purpose other than this study, and study drug accountability must be maintained for all bottles distributed to the investigative site.

Additional details regarding study drug labeling and accountability can be found in the Pharmacy Manual.

5.3 Dosing Regimen

Subjects will take a loading dose (3 tablets taken orally) at the site on the first day of the treatment period (Study Day 1). Starting on Study Day 2, subjects will take one tablet per day taken orally. Subjects will be instructed to take all doses from Study Day 2 onward once a day. Study drug may be taken with or without food.

5.4 Dose Modification

No dose modification of study drug will be allowed during this study.

5.5 Missed or Delayed Doses

Each dose of study drug after the first dose must be administered once daily. If a dose is missed, that dose will be considered and documented as a missed dose. Dosing should resume the next day.

5.6 Study Drug Discontinuation

Subjects should be discontinued from study drug treatment in the following situations:

- A female subject desires to become pregnant at the current time, stops contraception or expels her intrauterine device/implant, or becomes pregnant
- A female subject has new breast findings (e.g. a palpable mass or abnormal mammography, discharge), or has abnormal vaginal discharge or bleeding
- The subject decides to discontinue study drug treatment, or withdraws consent from the study
- The subject receives a strong CYP3A4 inhibitor (See [Appendix B](#))

- Any medical condition that may jeopardize the subject's safety if study drug is continued, in the investigator's and/or Sponsor's opinion; this may include the development of persistently (2 successive occasions) abnormal thyroid function tests (TSH >10, or TSH > 6 with low free T4; TSH <0.1, or TSH < 0.35 with high free T4); abnormal morning prolactin, cortisol, or corticotropin levels; or signs and symptoms of adrenal insufficiency
- Discontinuation is deemed to be in the best interest of the subject, in the investigator's and/or Sponsor's opinion, including evidence that the subject does not meet inclusion/exclusion criteria intended primarily for safety reasons, or a persistent lack of adherence to study procedures

The Sponsor or designee should be contacted within 24 hours of investigator's awareness of any study drug treatment discontinuation. Investigators should make every effort to contact the Sponsor or designee before discontinuing study drug treatment, if possible.

Subjects who discontinue treatment with study drug prior to completing the treatment period will enter a 5-week follow-up period following the last dose of study drug in addition to a Follow-up visit (see [Section 3.1](#), [Section 6.5.10](#)). Every effort should be made for subjects to complete the Follow-up visit after a subject has discontinued from study drug.

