Statistical Methods:	Efficacy analyses will be based upon an intent-to-treat philosophy. The primary

	
efficacy population will be the Intent-to-Treat (ITT) population that will include all randomized subjects who were dispensed study drug. Analyses performed on the Per Protocol population will be considered supportive. Subjects will be analyzed within the treatment group to which they are randomized.
 
Efficacy Analyses:
 
The primary efficacy endpoint is a binary variable taking on values of responder or non-responder. Subjects will be considered a responder if they have at least a 4-point reduction in WI-NRS between baseline and Week 10. Missing data imputation will be used for subjects who fail to complete the eDiary at Week 10, unless the subject withdrew from the study due to a lack of efficacy, or the subject used an excluded therapy to treat worsening of pruritus or PN, in which case their responder status will be defined as non-responder. The primary endpoint will be summarized with descriptive statistics by treatment group and study week.
 
The difference in the primary efficacy outcome measure between treatment groups will be tested using a Cochran Mantel Haenszel test controlling for the stratification factors. Testing of the key secondary efficacy endpoints will also be employed.

Study Sites:	Approximately 50 study sites.
Expected Duration of Subject's Participation	15-19 weeks: 2-4 weeks of screening, 10 weeks of treatment, and a follow-up period of 3 or 5 weeks.

This study will be conducted in accordance with the Guidelines of Good Clinical Practice (GCP).

TABLE OF CONTENTS

CLINICAL STUDY PROTOCOL	1
SIGNATURE PAGE FOR PRINCIPAL INVESTIGATOR(S).....	2
SPONSOR PROTOCOL APPROVAL SIGNATURE(S).....	3
PROTOCOL SYNOPSIS.....	4
TABLE OF CONTENTS.....	9
LIST OF APPENDICES.....	12
LIST OF FIGURES	13
LIST OF TABLES.....	13
LIST OF ABBREVIATIONS AND DEFINITIONS OF TERMS.....	14
1 INTRODUCTION	16
1.1 Pruritus in Prurigo Nodularis.....	16
1.2 Conditions Associated With Prurigo Nodularis.....	16
1.3 Current Treatment Options for Prurigo Nodularis.....	17
1.4 Substance P and the Neurokinin-1 Receptor	17
1.5 Serlopitant.....	18
1.5.1 Serlopitant Background and Nonclinical Summary	18
1.5.2 Serlopitant Clinical Summary.....	19
1.5.3 Serlopitant in Pruritus-Related Studies.....	19
2 STUDY OBJECTIVES.....	21
3 STUDY DESIGN.....	21
3.1 Overall Study Design.....	21
3.2 Rationale for Study Design and Dose Selection.....	22

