All screening procedures must be completed within 31 days before the Baseline visit. The minimum screening period for all subjects is 14 days to allow for collection of electronic diary (eDiary) screening data. Subjects who require screening period longer than 14 days will have a telephone contact at least 15 days prior to the scheduled Baseline visit to remind them to complete the eDiary as previously instructed at the Screening visit.

Screening procedures may be deferred following discussion with the medical monitor should more than 31 days be required (e.g. to wash out of certain excluded therapies or to treat their underlying condition).

Screening procedures may be repeated (i.e., the subject may be rescreened) following discussion with the medical monitor should the subject have had difficulty complying with eDiary assessments, require further training in the assessments, or have other relevant needs that may delay enrollment in the study but are not expected to impact safety or efficacy assessments.

Subjects will be provided an eDiary at the Screening visit. Subjects must be willing and able to complete the eDiary every day within a consistent timeframe, and comply with restrictions on allowable concomitant therapies, for the duration of the study.

At the Baseline visit (Day 1), eligible subjects will be randomly assigned to receive study drug (serlopitant 5 mg or placebo). Subjects will take a loading dose (3 tablets taken orally) at the site on the first day of the treatment period (Day 1). Starting on Day 2, subjects will take one tablet per day. Study drug may be taken with or without food.

The primary efficacy endpoint will be assessed at Week 10 of treatment.

Subjects who complete the 10-week treatment period and required follow-up period may be given the opportunity to enroll in a one-year open-label safety study (MTI-107) with daily oral doses of serlopitant 5 mg.

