6.5.10 Follow-up Visit

The required Follow-up visit occurs 21 or 35 (+7 days) after the Week 10 visit or the last dose of study drug for subjects who discontinue study drug early. The required follow-up period is defined as a minimum of 3 weeks for those subjects who will enroll in the one-year open-label safety study on the date of the follow-up visit, and as 5 weeks for those subjects who will not be enrolled in the one-year open-label safety study of serlopitant. Should a subject present for the follow-up visit prior to 5 weeks after the last dose of study drug and be excluded from participation in the one-year study for any reason, the subject will be required to return at 5 weeks after the last dose of study drug for a complete follow-up visit.

At the Follow-up visit, the following procedures and assessments are to be performed:

- Register visit into the IWRS
- Ask the subject to complete the HADS and ESS questionnaires
- Assess and record any changes in the subject's concomitant medications
- Female subjects should be queried for presence of new breast masses or abnormal discharge, and abnormal vaginal bleeding or discharge
- Review menstrual diary and record dates of menstrual flow (if applicable)
- Obtain vital signs

- Perform targeted physical examination, including weight
- Perform IGA PN-A
- Perform IGA PN-S
- Obtain ECG
- Obtain photos (at selected sites, only subjects that signed photography consent)
- Perform a urine pregnancy test for females of childbearing potential (with positive or equivocal results confirmed by a serum pregnancy test)
- Draw blood for clinical laboratory tests (morning blood sampling due to Endocrine assessments)
 - Reproductive endocrine labs for females under 55 years of age at consent
 - Endocrine
 - Hematology
 - Chemistry
- Assess and record any AEs and SAEs
- Collect eDiary device, review eDiary for compliance

6.5.11 *Early Termination*

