8.2 Handling of Missing Data

Should a determination of treatment period (on treatment, pre-treatment, follow-up) be required for adverse events or concomitant medication but the corresponding date is missing, or is a partial date, the event/medication will be considered on treatment unless the portions of the date that are available indicate this is not possible.

The primary method of handling missing efficacy data will be MCMC multiple imputation. Subjects who withdrew from the study due to a lack of efficacy, or used an excluded therapy to treat worsening of pruritus or PN, will be defined as non-responder. Imputation will be conducted within each treatment group independently, so the pattern of missing observations in one treatment group cannot influence missing value estimations in another. For each imputation process, 25 imputations will be performed.

If a subject fails to complete their eDiary for the week prior to Week 10, the primary endpoint (WI-NRS) data will be missing, unless the subject withdrew from the study due to a lack of efficacy, or the subject used an excluded therapy to treat worsening of pruritus or PN, in which case their responder status will be defined as non-responder. If the Week 10 value is missing for any other reason, the change from baseline value will be based on imputed data. Missing Week 10 WI-NRS values from which the 4-point responder status is derived will be estimated by MCMC.

Missing WI-NRS data will be derived for the analysis using the method of MCMC multiple imputation. Since both primary and key secondary efficacy endpoints require WI-NRS, the following steps will be followed:

1. Using the daily eDiary data, calculate Baseline and Week 2 through Week 10 values by averaging available values. In order to compute a week's average, a minimum of 4 values must be available for that week. The weekly average will be imputed when there are fewer than 4 values available.
2. From step 1, create a dataset for each treatment group, of subjects with observed values and those needing estimation by MCMC. The missing WI-NRS values in each dataset will be filled in using the MCMC method to generate 25 datasets. The resulting datasets for each treatment arm will be combined into one complete dataset.

Syntax:

```
proc mi data=datain out=dataout seed=&seed. Nimpute=25 <options>;  
  where trtpn=(TRT); /* Note TRT = [1, 2]; depending on treatment group */;  
  mcmc chain=single;  

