APPENDIX A SCHEDULE OF ACTIVITIES AND ASSESSMENTS

Table 2 Schedule of Visit Activities

Examination	Screening	Mid-Screening ^{1C}	Baseline ¹	Week 1 ^{1C} (± 3 days)	Week 2 (± 3 days)	Week 4 (± 3 days)	Week 6 (± 3 days)	Week 10 (± 7 days)	F/U ²	Early Treatment Discontinuation
Demographics	X									
Informed consent	X									
WI-NRS ³	X	X	X	X	X	X	X	X		
DLQI			X			X		X		X
HADS, ESS			X			X		X	X	X
ECG	X				X	X		X	X	X
Vital signs	X		X		X	X	X	X	X	X
Medical history (and prior medications)	X	X	X							
Physical exam ⁴	X		X		X	X	X	X	X	X
Concomitant medications			X	X	X	X	X	X	X	X
Labs ⁵	X				X			X	X	X
Urine pregnancy test ⁶	X		X			X	X	X	X	X
PK blood draw					X	X		X		
Review of I/E criteria	X	X	X							
IGA PN-A and IGA PN-S			X		X	X		X	X	X
Photography (selected sites)			X					X	X	X
Dispense/review menstrual diary (if applicable)	X		X		X	X	X	X	X	X
Dispense/collect eDiary	X								X	X
eDiary review/compliance ⁷		X	X	X	X	X	X	X	X	
Dispense and/or collect study drug			X		X	X	X	X		X
Review study drug compliance					X	X	X	X		
AEs/SAEs ⁸	X	X	X	X	X	X	X	X	X	X

^{1C}Telephone Contact: The Mid-Screening telephone contact should only occur for subjects who require a washout longer than 2 weeks, at least 15 days prior to the scheduled Baseline visit.

¹All visits and windows should be scheduled based on the Baseline Visit (Day 1)

²The Follow-up (F/U) visit occurs 21-35 days (+ 7 days) after the Week 10 visit or the last dose of study drug for subjects who discontinue study drug early.

³WI-NRS at Screening visit will be collected manually on paper for Inclusion/Exclusion criteria. All subsequent WI-NRS are collected daily via eDiary.

⁴Screening physical exam is complete and includes height and weight; other physical exams are targeted and include weight.

⁵Labs are ideally performed in the morning, particularly at visits with endocrine assessments (including Reproductive Endocrinology for females under 55 at age of consent) at Screening, Week 10 and Follow Up. Iron Studies, serum IgE and Serology labs are done only at Screening visit; endomysial antibody test and other optional studies only performed at Screening;

⁶Female subjects of childbearing potential only. Serum pregnancy test is required for positive or equivocal results

⁷See Table 3 for eDiary assessments

⁸During the period between informed consent and first study drug dose, only SAEs caused by a protocol-mandated intervention will be collected.

Table 3 **Schedule of eDiary Assessments**

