An eDiary device is provided to subjects at the Screening visit and collected at the Follow-up visit.

Device	Assessment	Frequency and Duration of Assessment
eDiary	WI-NRS	Once daily from Screening/Mid-Screening visit through the Follow-up visit
eDiary	Dosing	Once daily from Baseline visit through Week 10 visit or study drug discontinuation

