6.1.3 Visit Windowing

Data will be summarized based on nominal visit indications. Data collected during post-treatment follow-up will be summarized as

Protocol Version(s)	Nominal Visit	Analysis Visit
V2.0; V2.1	3-Week Follow-up	3-Week Follow-up
V2.0; V2.1	5-Week Follow-up	5-Week Follow-up

In addition, a “Latest Follow-up” visit will be summarized, which will include the latest available follow-up information for each subject from the 3-, 5- Week Follow-up visits.

Information collected at early treatment discontinuation visits will be mapped to the most appropriate visit based on the midpoints between scheduled visits.

For example, if a subject terminates use of study drug on or after Day 22 but before Day 36, data collected at the early end of treatment visit will be mapped to the Week 4 evaluation for summaries. If the subject has Week 4 values present, the data collected at the early end of

treatment visit will not replace the data collected at Week 4. For the sensitivity efficacy analyses, last observation carried forward (LOCF) will be applied subsequent to mapping the information to the appropriate visit.

Additionally, WI-NRS will be summarized at Weeks 1, 2, 3, 4, 5, 6, 7, 8, 9, 10 and 3- and 5-Week Follow-up by averaging the daily results for the 7 days prior to each week. The weekly average values will be calculated if a subject has at least four responses during the 7 day range, as defined below:

Week/Visit	Study Day Range
Week 1	2-7 (as Day 1 may be pre or post first dose)
Week 2	8-14
Week 3	15-21
Week 4	22-28
Week 5	29-35
Week 6	36-42
Week 7	43-49
Week 8	50-56
Week 9	57-63
Week 10	64-70
3-Week Follow-up	Post-treatment days 15-21
5-Week Follow-up	Post-treatment days 29-35

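### Follow-up of early stoppers is timed from the last dose, so a subject who stops by Day 24 (Day 31 on the nominal schedule) for a reason not scored as failure cannot have an observed Week 10 score and is imputed with no account of being off drug

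*Protocol*

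**What the plan says.** Protocol v4.0 section 5.6 provides that subjects who stop study drug early "will enter a 5-week follow-up period following the last dose of study drug in addition to a Follow-up visit". Section 6.5.10 sets the timing: "The required Follow-up visit occurs 21 or 35 (+7 days) after the Week 10 visit or the last dose of study drug" for those who stop early. The 21-day option is for subjects entering the open-label study, which section 3.1 offers to treatment completers ("Subjects who complete the 10-week treatment period and required follow-up period may be given the opportunity to enroll"). It therefore does not apply to early stoppers, whose visit falls 35 to 42 days after the last dose. No section keeps them on visits or on the diary to Week 10.

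Appendix A gives two answers on the diary. Table 3 runs WI-NRS entry "Once daily from Screening/Mid-Screening visit through the Follow-up visit". Table 2, in the row "Dispense/collect eDiary", also marks the Early Treatment Discontinuation column.

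SAP 6.1.3 defines Week 10 as Study Days 64-70 and states "The weekly average values will be calculated if a subject has at least four responses during the 7 day range". Protocol 8.2 has the same minimum: "In order to compute a week's average, a minimum of 4 values must be available for that week". The windows go by study day, with no condition that the subject is on drug. A missing weekly value is imputed by MCMC separately in each arm, from baseline and Weeks 1-10 (protocol 8.2, SAP 6.1.5). Lack of efficacy and use of excluded therapy for worsening are scored as non-response (protocol 8.2, SAP 6.1.5 and 6.7). The v4.0 synopsis says: "Efficacy analyses will be based upon an intent-to-treat philosophy".

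**The concern.** For the subjects who stop soonest, data collection can end before the primary time point. Whether a stopper has an observed primary outcome then depends on the stop date. A subject who stops for an adverse event on Day 20 is imputed. One who stops for the same reason on Day 35 and keeps the diary is scored on real off-drug values.

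The imputation model has no term for being off drug and is fitted largely to subjects still taking it. If the drug works, imputed values for early serlopitant stoppers lean towards the on-drug response of their arm, which flatters serlopitant. It also sits poorly with the intent-to-treat aim, which calls for the outcome at Week 10 whether or not treatment continued.

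**Working it through.** **The plan's own figure.** The documents state more than 90% power for 280 subjects. The assumed rates are redacted in protocol 8.1 and SAP section 7, so this cannot be reproduced, and the timing result does not depend on it. With 140 per arm, a two-sided 5% test and an assumed 25% on placebo, 90% power needs about 43% on serlopitant. I use 43% as the on-drug rate.

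**Timing.** Let L be the study day of the last dose.

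- Last diary day, if the diary runs to the Follow-up visit (Table 3): L + 35, or up to L + 42 with the +7 window.
- Last diary day needed for 4 entries in Days 64-70: Day 67 or later.
- Nominal visit: L ≥ 67 − 35 = Day 32.
- Latest visit: L ≥ 67 − 42 = Day 25.

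| Last dose (day) | Diary ends (day) | Week 10 entries available |
|---|---|---|
| 14 | 49 to 56 | 0 |
| 24 | 59 to 66 | 0 to 3 |
| 25 | 60 to 67 | 0 to 4 |
| 28 | 63 to 70 | 0 to 7 |
| 31 | 66 to 73 | 3 to 7 |
| 32 | 67 to 74 | 4 to 7 |

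The bar is therefore absolute to Day 24, depends on the visit date for Days 25-31, and is gone from Day 32. If no entry is made on the visit day itself, each cut-off moves one day later. If the device is collected at discontinuation (Table 2), nobody whose discontinuation visit falls before Day 67 can have an observed score.

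**Size.** Overstatement of the serlopitant rate = k × (imputed response − true off-drug response) / 140, where k is the number affected. Assumptions, none from the documents: k = 7 or 14 (5% or 10% of 140), and true off-drug response 10% or 25%.

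*Device collected at discontinuation.* Simulating within-arm regression imputation when entries end at stopping gives an imputed response of roughly 41-45%, in effect the arm's own 43%.

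- k = 7: 7 × (0.43 − 0.25)/140 = 0.9 points; 7 × (0.43 − 0.10)/140 = 1.65 points.
- k = 14: 14 × 0.18/140 = 1.8 points; 14 × 0.33/140 = 3.3 points.

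*Diary kept to the Follow-up visit.* About five off-drug weeks of the subject's own scores now enter as predictors. Simulations with stops in about the first 24 days and several assumed within-subject correlation structures give an imputed response of 15-27% against a true 10%, and 28-37% against a true 25%.

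- k = 7: from 7 × (0.28 − 0.25)/140 = 0.15 to 7 × (0.27 − 0.10)/140 = 0.85 points.
- k = 14: from 14 × 0.03/140 = 0.3 to 14 × 0.17/140 = 1.7 points.

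The range is about 0.2-1.7 points. It is near zero if itch returns fully and quickly to baseline, because the off-drug weeks then show it.

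**The case against.** The strongest reply is that the group is small and partly provided for.

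- **Who is affected.** A reader might infer that everyone who stops early is imputed. The documents do not support that: SAP 6.7 scores stopping for lack of efficacy, and excluded therapy for worsening, as non-response. These are the reasons most closely tied to itch. What remains is adverse events, subject, investigator or sponsor decisions, pregnancy, a strong CYP3A4 inhibitor and the like.
- **What the imputation does.** A reader might also infer that these subjects are imputed as if still on drug. That fits only if the device is handed back at discontinuation. Under Table 3 their own off-drug weeks pull the imputed value down, and the 0.9-3.3 point range does not apply.
- **How many.** The 5-10% is an assumption. In the Phase 2 PN study (protocol 1.5.3), 3 serlopitant and 6 placebo subjects of 128 randomised 1:1 discontinued for treatment-emergent adverse events. That is about 3/64 = 5% on serlopitant over 8 weeks, not 4, though it counts adverse events only.
- **Sensitivity analyses.** The tipping-point analysis (SAP 6.8.3) varies the successes among subjects with missing data in both arms, so it covers the off-drug response rates considered here.

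All of this stands and limits the size. It does not remove the gap. The tipping point shows how strong an assumption must be to change the result, but not what happened to these subjects. LOCF carries an earlier value forward, and the repeated measures model uses only what was recorded. None of them replaces data that were never collected.

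**Conclusion.** The point holds in limited form. On the documents' own dates, a last dose by Day 24, or by Day 31 with the Follow-up visit on its nominal day, rules out an observed Week 10 score. This matters for subjects not already non-responders by rule. Later stoppers who keep the diary are scored on off-drug values, so the same event is handled differently according to its date.

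The likely bias is modest: about 0.2-1.7 points on the serlopitant rate if Table 3 governs, and about 0.9-3.3 points if Table 2 does. Against an assumed difference of 43% − 25% = 18 points, the upper ends are 1.7/18 = 9% and 3.3/18 = 18% of the effect. The difference between arms shifts by the same amount only if placebo stoppers are imputed without bias. The timing result rests on the text alone; the sizes rest on assumed stop rates and off-drug response. This is a change that should be made, at the lower end of that grade, chiefly because it is cheap.

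**What to change.** 1. In protocol 5.6, 6.5.10 and Appendix A Tables 2 and 3, have subjects who stop study drug early but remain in the study continue daily WI-NRS entry, remotely, through Study Day 70 or the Follow-up visit, whichever is later.
2. Reconcile Table 2, which marks eDiary collection at Early Treatment Discontinuation, with Table 3. Correcting Table 2 alone would still leave stops to Day 24 without an observable endpoint.
3. In SAP 6.1.3 and 6.1.5, use the observed Days 64-70 score for every early stopper who is not a non-responder by rule, and keep imputation for those who stop reporting.
4. State in the SAP how the Week 10 score is handled when a therapy permitted in follow-up was started for pruritus or PN before Day 70. Protocol 5.7.2 permits some topical and anti-pruritic therapies in that period, and the current rule names only excluded therapy. One option is to score such a subject as a non-responder, as for excluded therapy. Without a rule, step 3 could count as response an improvement due to another treatment.

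The cost is amendment wording, a few extra weeks of a one-question diary for a small number of subjects, later return of devices and some refusals.
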